3.2.2.3. Vital Signs

Supine blood pressure (BP) and pulse rate will be measured at times specified in the SoA given in the protocol.

For each period, the baseline measurement is the last predose measurement on Day 1. Changes from baseline will be defined as the change between the postdose and baseline measurements.

3.2.2.4. Electrocardiograms

QT interval, QTcF, PR, QRS and heart rate (HR) will be recorded at each assessment time indicated in the SoA given in the protocol. QTcF will be derived using Fridericia's heart rate correction formula:

$$\text{QTcF} = \text{QT} / (\text{RR})^{1/3} \text{ where RR} = 60/\text{HR} \text{ (if not provided)}$$

For each period, the baseline measurement is the last predose measurement on Day 1. Changes from baseline will be defined as the change between the postdose and baseline measurements.

3.3. Other Safety Endpoints

None.

3.4. Exploratory Endpoints

Exploratory endpoints are additional plasma PK parameters of sisunatovir (CL/F, V_z/F, T_{max}, t_{1/2}) as PIC or WGT in a fasted state, or as WGT in a fed state.

3.5. Baseline Variables

Baseline characteristics will be collected according to the SoA as specified in the protocol.

4. ANALYSIS SETS (POPULATIONS FOR ANALYSIS)

Data for all participants will be assessed to determine if participants meet the criteria for inclusion in each analysis population prior to releasing the database and classifications will be documented per standard operating procedures.

For purposes of analysis, the following analysis sets are defined:

Participant Analysis Set	Description
Enrolled	“Enrolled” means a participant’s agreement to participate in a clinical study following completion of the informed consent process and randomization/assignment to study intervention. A participant will be considered enrolled if the informed consent is not withdrawn prior to participating in any study activity after screening. Potential participants who are screened for the purpose of determining eligibility for the study, but do not participate in the study, are not considered enrolled, unless otherwise specified by the protocol.
Evaluable	All participants randomly assigned to study intervention and who take at least 1 dose of study intervention.
Safety	All participants randomly assigned to study intervention and who take at least 1 dose of study intervention. Participants will be analyzed according to the product they actually received.
PK Parameter Set	All randomized participants who receive at least one dose of study medication and in whom at least 1 plasma PK parameter is calculated.
PK Concentration Set	All randomized participants who receive at least 1 dose of study medication and in whom at least 1 plasma concentration value is reported.

5. GENERAL METHODOLOGY AND CONVENTIONS

Final analysis will be performed after study participant data set release following last participant last visit.

5.1. Hypotheses and Decision Rules

No statistical hypothesis will be tested in this study.

5.2. General Methods

5.2.1. Analyses for Binary/Categorical Endpoints

For binary or categorical variables, number of participants, numbers and percentages of participants meeting the categorical criteria will be presented in accordance with the Clinical Data Interchange Standards Consortium and Pfizer Standards (CaPS).

5.2.2. Analyses for Continuous Endpoints

For continuous variables, the data will be summarized using the number of participants, mean, median, standard deviation (SD), minimum, and maximum in accordance with the CaPS. For appropriate PK parameters, geometric mean and geometric coefficient of variation (%CV) will also be summarized.

5.3. Methods to Manage Missing Data

5.3.1. Pharmacokinetic Data

Methods to handle missing PK data are described below.

Concentrations Below the Limit of Quantification:

In all data presentations (except listings), concentrations below the limit of quantification (BLQ) will be set to zero. (In listings BLQ values will be reported as “<LLQ”, where LLQ will be replaced with the value for the lower limit of quantification.).

Deviations, Missing Concentrations and Anomalous Values:

In summary tables and plots of median profiles, statistics will be calculated having set concentrations to missing if one of the following cases is true:

1. A concentration has been collected as ND (ie, not done) or NS (ie, no sample).
2. A deviation in sampling time is of sufficient concern or a concentration has been flagged as anomalous by the pharmacokineticist.

Note that summary statistics will not be presented at a particular time point if more than 50% of the data are missing.

An anomalous concentration value is one that, after verification of bioanalytical validity, is grossly inconsistent with other concentration data from the same individual or from other participants. For example, a BLQ concentration that is between quantifiable values from the same dose is considered as anomalous. Anomalous concentration values may be excluded from PK analysis at the discretion of the PK analyst or pharmacokineticist.

PK Parameters:

Actual PK sampling times will be used in the derivation of PK parameters. If a PK parameter cannot be derived from a participant's concentration data, the parameter will be coded as NC (ie, not calculated). (Note that NC values will not be generated beyond the day that a participant discontinues). In summary tables, statistics will be calculated by setting NC values to missing; and statistics will be presented for a particular treatment with ≥ 3 evaluable measurements. PK parameter analyses will not be performed for a particular parameter if more than 50% of the data are NC.

If an individual participant has a known biased estimate of a PK parameter (due for example to an unexpected event such as vomiting before all the compound is adequately absorbed from the gastrointestinal tract), this will be footnoted in summary tables and will not be included in the calculation of summary statistics or statistical analyses.

5.3.2. Safety Data

Missing values in standard summaries of safety data will be imputed according to CaPS.

6. ANALYSES AND SUMMARIES

The plasma concentrations of sisunatovir will be listed and descriptively summarized by nominal PK sampling time and treatment on the PK Concentration Set. Individual participant and summary profiles (mean and median plots) of the plasma concentration-time data will be plotted by treatment using actual and nominal times, respectively. Mean and median profiles will be presented on both linear and semi-log scales.

Presentations for sisunatovir concentrations will include:

- A listing of all concentrations sorted by participant ID, treatment and nominal time postdose. The concentration listing will also include the actual times. Deviations from the nominal time will be given in a separate listing.
- A summary of concentrations by treatment and nominal time postdose, where the set of statistics will include n, mean, median, SD, %CV, minimum, maximum and the number of concentrations above the LLQ.
- Median concentrations time plots (on both linear and semi-log scales) against nominal time postdose by treatment (all treatments on the same plot per scale, based on the summary of concentrations by treatment and time postdose).
- Mean concentrations time plots (on both linear and semi-log scales) against nominal time postdose by treatment (all treatments on the same plot per scale, based on the summary of concentrations by treatment and time postdose).
- Individual concentration time plots by treatment (on both linear and semi-log scales) against actual time postdose (there will be separate spaghetti plots for each treatment per scale).
- Individual concentration time plots by participant (on both linear and semi-log scales) against actual time postdose [there will be separate plots for each participant (containing all treatments) per scale].

The PK parameters will be summarized descriptively by treatment group in accordance with Pfizer data standards on the PK Parameter Set, as data permit. Missing values will be handled as detailed in [Section 5.3.1](#). Each PK parameter will be summarized by treatment group and will include the set of summary statistics as specified in [Table 5](#).

Table 5. PK Parameters to be Summarized Descriptively by Treatment

Parameter	Summary Statistics
AUC _{inf} , AUC _{last} , C _{max} , CL/F, V _z /F	N, arithmetic mean, median, SD, %CV, minimum, maximum, geometric mean and geometric %CV
T _{max}	N, median, minimum, maximum
t _{1/2}	N, arithmetic mean, median, SD, %CV, minimum, maximum

The following supporting data from the estimation of t_{1/2} will be listed by treatment group: the terminal phase rate constant (k_{el}); goodness-of-fit statistic from the regression (r²); the percentage of AUC_{inf} obtained by forward extrapolation (AUC_{extrap}%); and the first, last, and number of time points used in the estimation of k_{el} (k_{el,t(1)}, k_{el,t(2)}, and k_{el,t(n)}).

6.1. Primary Endpoints

Plasma AUC_{last}, AUC_{inf} (if data permit) and C_{max} will be summarized descriptively by treatment. Box and whisker plots for AUC_{last}, AUC_{inf} (if data permit) and C_{max} will be plotted by treatment.

For the estimation of rBA of sisunatovir **CCI** mg as WGT compared to sisunatovir **CCI** mg as PIC in a fasted state, *natural log transformed AUC_{last}, AUC_{inf} (if data permit) and C_{max} will be analyzed separately using a mixed effect model with sequence (AB or BA), period and treatment included as fixed effects and participant nested within sequence as a random effect. Only data from the first 2 study periods will be used in the analysis. Estimates of the adjusted mean differences (Test-Reference) and corresponding 90% CIs will be obtained from the model. The adjusted mean differences and 90% CIs for the differences will be exponentiated to provide estimates of the ratio of adjusted geometric means (Test/Reference) and 90% CIs for the ratios. Treatment A is the Reference treatment and Treatment B is the Test treatment.*

Residuals from the model will be examined for normality and the presence of outliers via visual inspection of plots of residuals vs predicted values and normal probability plots of residuals but these will not be included in the CSR. If there are major deviations from normality or outliers then the effect of these on the conclusions will be investigated through alternative transformations and/or analyses excluding outliers. Justification for any alternative to the planned analysis will be given in the report of the study.

6.2. Secondary Endpoints

6.2.1. Food Effect PK Data

For the secondary endpoints on the assessment of high-fat food effect, *natural log transformed AUC_{last}, AUC_{inf} (if data permit) and C_{max} of sisunatovir will be analyzed using a mixed effect model with sequence and treatment as fixed effects and participant within sequence as a random effect. Estimates of the adjusted mean differences (Test-Reference) and corresponding 90% CIs will be obtained from the model. The adjusted mean differences and 90% CIs for the differences will be exponentiated to provide estimates of the ratio of adjusted geometric means (Test/Reference) and 90% CI for the ratios. Treatment B (WGT under fasted condition) is the Reference treatment and Treatment C (WGT with a high-fat*

meal) is the Test treatment. Only the data from Treatments B and C will be included in the model.

For the secondary endpoints on the assessment of the low-fat food effect, natural log transformed AUC_{last} , AUC_{inf} (if data permit) and C_{max} of sisunatovir will be analyzed using a mixed effect model with sequence and treatment as fixed effects and participant within sequence as a random effect. Estimates of the adjusted mean differences (Test-Reference) and corresponding 90% CIs will be obtained from the model. The adjusted mean differences and 90% CIs for the differences will be exponentiated to provide estimates of the ratio of adjusted geometric means (Test/Reference) and 90% CI for the ratios. Treatment B (WGT under fasted condition) is the Reference treatment and Treatment D (WGT with a low-fat meal) is the Test treatment. Only the data from Treatments B and D will be included in the model.

Residuals from the model will be examined for normality and the presence of outliers via visual inspection of plots of residuals vs predicted values and normal probability plots of residuals but these will not be included in the CSR. If there are major deviations from normality or outliers then the effect of these on the conclusions will be investigated through alternative transformations and/or analyses excluding outliers. Justification for any alternative to the planned analysis will be given in the report of the study.

Exploratory analyses may be performed to assess rBA of sisunatovir for participants who participated in both part 1 and part 2 of the study. These data will be used for internal exploratory purposes and will not be included in the clinical report.

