All study interventions will be administered as a single dose of **CCI**-mg sisunatovir as WGT.

B = WGT under fasted condition; D= WGT with a low-fat meal.

Part 2 consists of an initial screening period of up to 28 days, a 7-day inpatient stay at the CRU which includes 2 periods, and a follow-up contact that will occur 28-35 days after the last administration of sisunatovir. For individual participants, the total duration of participation from the screening visit to the follow-up visit or phone call will range from approximately 6 weeks (minimum) to approximately 10 weeks (maximum).

Approximately 12 participants will be randomized into 2 sequences with approximately 6 participants in each. For each sequence, participants will receive study interventions in a pre-specified manner as listed in Table 7.

Participants who discontinue from the study for non-safety reasons may be replaced at the sponsor's discretion in collaboration with the investigator.

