4.2. Scientific Rationale for Study Design

The primary purpose of this study is to assess the relative bioavailability of sisunatovir **CCI** mg administered under fasted condition as WGT (a formulation intended for future clinical studies) vs PIC (a formulation used in C5241003, C5241005 and C5241006). In addition, food effect will be evaluated for the new WGT formulation. Therefore, it was originally designed to be a 3-period, cross-over study with 72 hours of washout between the dosing in Periods 1 and 2 or Periods 2 and 3.

Based on preliminary PK data from Part 1, a food effect was observed for WGT administered with high-fat meals compared to WGT administered under a fasted state. In order to have a thorough evaluation of the effects of meals on sisunatovir exposure, Part 2 is added to assess the oral PK of sisunatovir administered as WGT with low-fat meals compared to administered as WGT under a fasted state, in a 2-period cross-over design with at least 72 hours of washout between the dosing in Periods 1 and 2. Participants who have participated in Part 1 may also participate in Part 2.

In adults, the half-life of sisunatovir is ~7-10 hours in healthy participants. The effect of formulation on the PK of sisunatovir has been investigated in C5241001 (liquid versus DIC formulation) and C5241005 (PIC [DPB] dispersed in water vs DIC formulation). There is no indication of a change in half-life across formulations. Therefore, current study design with at least 72 hours of washout is supported by the $t_{1/2}$ ($>5 \times t_{1/2}$) between dosing in Periods 1 and 2 or Periods 2 and 3, which is considered adequate.

The effect of food on the PK of a single dose of sisunatovir **CCI** mg was investigated in C5241001 and C5241005, and appears to be formulation dependent (additional details in Section 2.2.4). As a novel formulation, the effect of food on the PK of sisunatovir administered as WGT will be assessed in this study to inform dose design for future studies.

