9.3.3.2. Other Secondary Endpoints Analyses

Part 1

To compare the Treatments A (PIC under fasted condition) and B (WGT under fasted condition), natural log transformed AUC_{last} , AUC_{inf} (if data permit) and C_{max} of sisunatovir will be analyzed separately using a mixed effect model with sequence (AB or BA), period and treatment included as fixed effects and participant nested within sequence as a random effect. Only data from the first 2 study periods will be used in the analysis. Estimates of the adjusted mean differences (Test-Reference) and corresponding 90% CIs will be obtained from the model. The adjusted mean differences and 90% CIs for the differences will be exponentiated to provide estimates of the ratio of adjusted geometric means (Test/Reference) and 90% CIs for the ratios. Treatment A is the Reference treatment and Treatment B is the Test treatment.

For the high-fat food effect evaluation, natural log transformed natural log transformed AUC_{last} , AUC_{inf} (if data permit) and C_{max} of sisunatovir will be analyzed using a mixed effect model with sequence, and treatment as fixed effects and participant within sequence as a random effect. Estimates of the adjusted mean differences (Test-Reference) and corresponding 90% CIs will be obtained from the model. The adjusted mean differences and 90% CIs for the differences will be exponentiated to provide estimates of the ratio of adjusted geometric means (Test/Reference) and 90% CI for the ratios. Treatment B (WGT under fasted condition) is the Reference treatment and Treatment C (WGT with high-fat meal) is the Test treatment. For the food effect comparison only the data from Treatments B and C will be included in the model.

Part 2

For the low-fat food effect evaluation, natural log transformed AUC_{last} , AUC_{inf} (if data permit) and C_{max} of sisunatovir will be analyzed using a mixed effect model with sequence, and treatment as fixed effects and participant within sequence as a random effect. Estimates of the adjusted mean differences (Test-Reference) and corresponding 90% CIs will be obtained from the model. The adjusted mean differences and 90% CIs for the differences will be exponentiated to provide estimates of the ratio of adjusted geometric means (Test/Reference) and 90% CI for the ratios. Treatment B (WGT under fasted condition) is the Reference treatment, Treatment D (WGT with low-fat meal) is the Test treatment.

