Participants who discontinue from the study for non-safety reasons may be replaced at the sponsor's discretion in collaboration with the investigator.

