Appendix 1. SAS Code for Analyses

An example of the PROC MIXED code is provided below:

For primary objective rBA (Periods 1 and 2):

```
proc mixed data=tab.pk;
  class seq period trt participant;
  model log&var=seq period trt/ ddfm=KR;
  random participant(seq) /subject=participant(seq);
  lsmeans trt;
  estimate 'B vs A' trt -1 1 /cl alpha=0.1;

  ods 'Estimates' out=est&var;
  ods 'lsmeans' out=ls&var;
  ods 'covparms' out=cov&var;
  ods 'tests3' out=tst&var;
run;
```

For secondary objectives high-fat and low-fat FE:

```
proc mixed data=tab.pk;
  class seq trt participant;
  model log&var= seq trt / ddfm=KR;
  random participant(seq) / subject=participant(seq);
  lsmeans trt;
  estimate 'C vs B' trt -1 1 /cl alpha=0.1;

  ods 'Estimates' out=est&var;
  ods 'lsmeans' out=ls&var;
  ods 'covparms' out=cov&var;
  ods 'tests3' out=tst&var;
run;

proc mixed data=tab.pk;
  class seq trt participant;
  model log&var= seq trt / ddfm=KR;
  random participant(seq) / subject=participant(seq);
  lsmeans trt;
  estimate 'D vs B' trt -1 1 /cl alpha=0.1;

  ods 'Estimates' out=est&var;
  ods 'lsmeans' out=ls&var;
  ods 'covparms' out=cov&var;
  ods 'tests3' out=tst&var;
run;
```

/* Letter assignments for treatments (trt) within the estimate statement above are as follows

A: Single dose of sisunatovir [REDACTED] mg as PIC under fasted condition;
 B: Single dose of sisunatovir [REDACTED] mg as WGT under fasted condition;
 C: Single dose of sisunatovir [REDACTED] mg as WGT with a high-fat meal.
 D: Single dose of sisunatovir [REDACTED] mg as WGT with a low-fat meal. */

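### The Part 2 low-fat food-effect model leaves out period although Part 2 is a randomised 2x2 crossover, so a period effect inflates the D/B interval and, if the sequences are unequal, biases the ratio.

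*SAP*

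**What the plan says.** Protocol 4.2 describes Part 2 as running "in a 2-period cross-over design with at least 72 hours of washout between the dosing in Periods 1 and 2", and the treatment tables in Protocol 4.1 and SAP 2.3 give the sequences BD and DB. On numbers, Protocol 4.1 says "Approximately 12 participants will be randomized into 2 sequences with approximately 6 participants in each", and SAP 2.3 adds "Participants who discontinue from the study for non-safety reasons may be replaced" at the sponsor's discretion.

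For the low-fat comparison of D with B, the second paragraph of SAP 6.2.1 says the log-transformed parameters will be "analyzed using a mixed effect model with sequence and treatment as fixed effects and participant within sequence as a random effect". Protocol 9.3.3.2 (Part 2) has the same "mixed effect model with sequence, and treatment as fixed effects and participant within sequence as a random effect", and so does the Synopsis. In SAP Appendix 1 the D vs B code is "model log&var= seq trt / ddfm=KR", and period is absent from its CLASS statement as well.

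The primary comparison of A with B, on Periods 1 and 2 of Part 1, is specified in SAP 6.1 with "sequence (AB or BA), period and treatment included as fixed effects and participant nested within sequence as a random effect".

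**The concern.** The plan treats two identical layouts differently. A vs B and D vs B are both two-sequence, two-period crossovers with randomised order, yet only the first is adjusted for period. The D vs B wording matches that of the Part 1 high-fat comparison. There C is always given in Period 3, so its effect cannot be separated from that of Period 3. Part 2 has no such constraint: B and D each occur in both periods, and period is fully estimable.

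In a 2x2 crossover a period shift raises D minus B in one sequence and lowers it by the same amount in the other. A sequence main effect describes a difference in participants' overall level, so it cannot take up this pattern. The shift therefore goes into the residual and makes the interval wider than it need be. If the sequences end unequal, part of it also goes into the D/B ratio. Allocation is only approximately six per sequence and replacement is optional, so inequality is plausible. The ratio and its 90% interval are the whole PK comparison that Part 2 delivers, and Protocol 4.2 says the food-effect assessment is to inform dosing in later studies.

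**Working it through.** **Inputs.** From Protocol 9.5: within-participant SD 0.34 (log AUC) and 0.38 (log Cmax), N = 12, 90% intervals whose width is met with 80% probability. The documents give no period effect, so Period 2/Period 1 ratios P of 1.0 to 1.5 are assumed. The check takes Part 2 data only, with both periods complete.

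**The plan's own figure.** Table 9 follows from

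log half-width = t(0.95, df) × SD × √(2/12) × √(χ²(0.80, df)/df).

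- With df = 10 (2x2 model with period), AUC: 1.812 × 0.34 × 0.408 × √(13.44/10) = 0.292. At a ratio of 100% this gives 75% to 134%, as printed. For Cmax it gives 0.326, or 72% to 139%, as printed. All 14 intervals reproduce to the whole percent.
- With df = 11 (sequence and treatment only), 2 of the 14 reproduce.

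**Estimate under the planned model.** With complete pairs it is the plain mean of the within-participant differences D − B. With p = ln P, each difference shifts by +p in BD and by −p in DB, so D/B is multiplied by

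P^((nBD − nDB)/(nBD + nDB)).

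At 7:5 and P = 1.25 this is 1.25^(2/12) = 1.038; at P = 1.5 it is 1.070. The direction reverses if DB is the larger sequence or if P is below 1.

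**Width at 6:6, AUC.** The expected variance of the differences is 2 × 0.34² + (12/11)p².

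- Planned: t(0.95, 11) × √((0.2312 + (12/11)p²)/12). For P = 1.25, p = 0.2231, this is 1.796 × √(0.2855/12) = 0.277. For P = 1.5, p = 0.4055, it is 0.332.
- With period: t(0.95, 10) × √(0.2312/12) = 1.812 × 0.1388 = 0.252, whatever P is.
- Ratios: 1.10 and 1.32.

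**Break-even at 6:6.** Equating the two gives p² = 2 × SD² × (11/12) × ((1.8125/1.7959)² − 1), hence P ≈ 1.06 for AUC and 1.07 for Cmax. Below this the planned interval is very slightly narrower, because it has one more degree of freedom.

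**Simulation (AUC, at least 100,000 runs per row).** Half-widths are simulated means on the log scale, slightly below the closed-form values, which use the expected variance.

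| BD:DB | P | D/B multiplied by | Half-width, planned | Half-width, with period | Width ratio | Coverage, planned |
|---|---|---|---|---|---|---|
| 6:6 | 1.0 | 1.000 | 0.243 | 0.245 | 0.99 | 90% |
| 6:6 | 1.1 | 1.000 | 0.249 | 0.245 | 1.01 | 91% |
| 6:6 | 1.25 | 1.000 | 0.271 | 0.245 | 1.10 | 93% |
| 6:6 | 1.5 | 1.000 | 0.326 | 0.245 | 1.33 | 97% |
| 7:5 | 1.1 | 1.016 | 0.249 | 0.249 | 1.00 | 90% |
| 7:5 | 1.25 | 1.038 | 0.270 | 0.249 | 1.09 | 92% |
| 7:5 | 1.5 | 1.070 | 0.324 | 0.249 | 1.30 | 95% |
| 6:4 | 1.1 | 1.019 | 0.277 | 0.280 | 0.99 | 90% |
| 6:4 | 1.25 | 1.046 | 0.301 | 0.280 | 1.08 | 92% |
| 6:4 | 1.5 | 1.085 | 0.361 | 0.280 | 1.29 | 94% |
| 8:4 | 1.25 | 1.077 | 0.268 | 0.260 | 1.03 | 89% |
| 8:4 | 1.5 | 1.145 | 0.318 | 0.260 | 1.22 | 88% |

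With period fitted, the bias factor is 1.00 and coverage 90% in every row. For Cmax at 6:6 the widening is 8% at P = 1.25 and 27% at P = 1.5; the bias factors do not depend on the SD.

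**The case against.** The omission itself is not in dispute; its size is.

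- **Small period effects do little.** At P = 1.1 the width changes by about 1% either way, and the bias is under 2% at 7:5 or 6:4. Single doses, confinement, standardised meals and dosing times, and a 72-hour washout against a half-life of 7 to 10 hours all point to a small effect. This stands. It makes the larger figures conditional on a period effect that nobody has yet reported.
- **The interval mostly stays conservative.** At 6:6 the ratio is unbiased, and at P = 1.25 coverage is still about 92% at 7:5 and 6:4. This stands too. Coverage falls below 90% to a notable degree only at a split such as 8:4, where the fault is under-coverage rather than excess width.
- **Table 9 does not show that period was intended for D vs B.** Protocol 9.5 does not name Part 2, and 10 degrees of freedom is what the primary model gives. This is fair. Table 9 shows only that the printed precision is that of a period-adjusted analysis, not of the Part 2 model as written.
- **Adding period costs more when sequences are unequal.** With no period effect, the mean width rises by about 0.7% at 6:6, 2.1% at 7:5, 3.2% at 6:4 and 6.8% at 8:4. This is correct and should be weighed against the bias removed.
- **The comparison is secondary and estimation-only**, with no hypothesis or limit to meet. That limits the severity. It is no reason to leave an estimable nuisance effect out of the model.

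**Conclusion.** The concern holds. The Part 2 model omits a term that the design can estimate and that the plan's own primary model includes, and no reason is given. Under the protocol's SD of 0.34 and an assumed period ratio of 1.25 to 1.5, the AUC interval at 6:6 is 10% to 33% too wide. At 7:5 the D/B ratio is off by 3.8% to 7.0%, and at 6:4 by 4.6% to 8.5%. For a period ratio near 1.1 or below, the consequence is negligible. The bias figures assume complete pairs; participants with only one period were not modelled. The change should be made, but the point is moderate: it concerns a secondary comparison, and at equal sequence sizes the estimate is unbiased.

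**What to change.** In the low-fat paragraph of SAP 6.2.1, list sequence, period and treatment as fixed effects. In the D vs B block of SAP Appendix 1, add `period` to both the CLASS and MODEL statements, as in the primary code. Align Protocol 9.3.3.2 (Part 2) and the Part 2 paragraph of the Synopsis. Leave the C vs B model as it is, with a sentence saying that treatment C is confounded with Period 3.

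The work is one model term and a few words. The statistical price is one residual degree of freedom (11 to 10 at N = 12) plus, when sequences are unequal, the loss of precision given above. Protocol 9 lets the SAP modify the planned analyses and calls for an amendment only for major changes to the primary endpoints or their analyses. A SAP revision recorded in SAP 2.1 could therefore suffice, with the protocol wording aligned at the next amendment. The revision should be made before the Part 2 data are analysed: the study is open-label, and a term added after the results are seen would look selective.

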Approximately 12 participants will be randomized into 2 sequences with approximately 6 participants in each. For each sequence, participants will receive study interventions in a pre-specified manner as listed in the table for Part 1 Study Design. Participants who

discontinue from the study for non-safety reasons may be replaced at the sponsor's discretion in collaboration with the investigator.

Part 2

Participants will be admitted to the CRU on Day -1 to undergo baseline procedures. All participants are planned to receive 1 dose of (B) sisunatovir [REDACTED] mg as WGT in a fasted state and 1 dose of (D) sisunatovir [REDACTED] mg as WGT with a low-fat meal. There is an at least 72-hour washout period between Period 1 and Period 2. Participants who have participated in Part 1 are eligible to participate in Part 2.

Part 2 Study Design

	Period 1	Period 2
Sequence 1 (N=6)	B	D
Sequence 2 (N=6)	D	B

All study interventions will be administered as a single dose of [REDACTED]-mg sisunatovir as WGT.
B = WGT under fasted condition; D= WGT with a low-fat meal.

Part 2 consists of an initial screening period of up to 28 days, a 7-day inpatient stay at the CRU which includes 2 periods, and a follow-up contact that will occur 28-35 days after the last administration of sisunatovir. For individual participants, the total duration of participation from the screening visit to the follow-up visit or phone call will range from approximately 6 weeks (minimum) to approximately 10 weeks (maximum).

Approximately 12 participants will be randomized into 2 sequences with approximately 6 participants in each. For each sequence, participants will receive study interventions in a pre-specified manner as listed in the table for Part 2 Study Design. Participants who discontinue from the study for non-safety reasons may be replaced at the sponsor's discretion in collaboration with the investigator.

Number of Participants:

Approximately 12 participants will be enrolled in Part 1 and approximately 12 participants will be enrolled in Part 2. Some participants may participate in both Parts 1 and 2, therefore the total number of participants in this study will be between approximately 12 and 24.

Note: "Enrolled" means a participant's agreement to participate in a clinical study following completion of the informed consent process and randomization/assignment to study intervention.

Study Population:

Key inclusion and exclusion criteria are listed below:

Inclusion Criteria

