9.3.1. General Considerations

Details of the analyses will be provided in the SAP.

All treatment arms will be reported separately.

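### Does the SAP leave open which Part's Treatment B records enter the food-effect models and the summaries?

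*SAP*

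**What the plan says.** SAP 2.3 gives fasted tablet dosing the letter B in both Parts: Part 1 uses sequences ABC and BAC, Part 2 uses BD and DB. The protocol synopsis adds that "Some participants may participate in both Parts 1 and 2", so the total is about 12 to 24 people.

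For the high-fat model SAP 6.2.1 says "Only the data from Treatments B and C will be included in the model"; for the low-fat model it says "Only the data from Treatments B and D will be included in the model". Neither sentence names a Part. In Appendix 1 all three model calls read the same dataset without a subset line, and the low-fat contrast is "estimate 'D vs B' trt -1 1 /cl alpha=0.1".

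The descriptive outputs are also keyed by treatment. SAP section 6 asks for mean and median plots with "all treatments on the same plot per scale, based on the summary of concentrations by treatment and time postdose", and for "A listing of all concentrations sorted by participant ID, treatment and nominal time postdose". SAP 6.1 adds box plots by treatment.

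On the other side stand protocol 9.3.1 ("All treatment arms will be reported separately") and protocol 9.3.3.2, which has separate Part 1 and Part 2 headings. Under the Part 1 heading it says "For the food effect comparison only the data from Treatments B and C will be included in the model"; the B and D model is under the Part 2 heading.

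**The concern.** The reference group for both food-effect ratios is Treatment B, and two sets of B records will exist. A programmer who filtered only on the letter would bring Part 1 fasted data into the low-fat comparison, or Part 2 fasted data into the high-fat one. That would mix a within-person crossover contrast with a comparison across study Parts, which were run at different times and perhaps in different people.

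The tables and plots raise a milder form of the question. If B were shown as one group, its row could hold up to 24 records beside about 12 each for A, C and D, and anyone in both Parts would count twice. The displayed B mean would then not be the reference mean behind either ratio. In the concentration listing, a person who kept one ID across Parts would have each nominal time twice under B.

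**Working it through.** **1. Which records belong to which model.**

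- High-fat: protocol 9.3.3.2 and the synopsis place B and C under Part 1. Treatment C exists only in Part 1.
- Low-fat: the same sections place B and D under Part 2. Treatment D exists only in Part 2.
- Primary: SAP 6.1 names the sequences AB and BA and the first two periods. Only Part 1 has these sequences.
- SAP 2.1 lists no modification of the protocol's analysis, so the protocol's Part headings carry over.
- The last paragraph of SAP 6.2.1 makes analyses of people in both Parts exploratory, internal and outside the clinical report. That fits only if the reported models stay within a Part.

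**2. The example code.** The contrast has two coefficients. With treatments A to D all present, -1 and 1 would fall on A and B, so the calls labelled C vs B and D vs B give those contrasts only on data already cut to two treatments. The primary call has no filter either, although it must be limited to Periods 1 and 2. The code assumes prepared data throughout.

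**3. The plan's own precision figure.** Inputs from protocol 9.5: within-participant log SD 0.34 (AUC) and 0.38 (Cmax), N = 12, 90% CI, 80% coverage probability. With 10 degrees of freedom,

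half-width = t(0.95; 10) × SD × √(χ²(0.80; 10)/10) × √(2/12).

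This gives 0.2917 for AUC and 0.3260 for Cmax. At a ratio of 100% the intervals are 74.7% to 133.9% and 72.2% to 138.5%, against the printed 75% to 134% and 72% to 139%. All 14 intervals in Table 9 reproduce. The standard error underneath for AUC is 0.34 × √(2/12) = 0.1388, which is the within-Part analysis of 12 people.

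**4. If the other Part's B records did slip in.** A generalised least squares check was run with sequence and treatment fixed and participant random. When sequence is identified by treatment order, as SAP 6.1 does for the primary model, the extra B records form sequence levels that contain only B. The sequence terms absorb them. Their weight in the D vs B contrast is 0 and the SE stays 0.1388, with or without overlap of people. For C vs B, checked without overlap, the result is the same.

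**5. If B were pooled in the summaries.** Assume 12 people per Part and no true difference between Parts. The pooled log mean is the average of the two Part means, so it differs from either by half their difference:

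SD = s × √(1/12 − 1/24) = 0.2041 × s.

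- *No overlap:* s is the total log SD. The documents give none for the fasted tablet. Protocol 2.2.4 gives a fasted AUCinf CV of 69.1% for PIC dispersed in water: s = √ln(1 + 0.691²) = 0.625, SD = 0.1276, or e^0.1276 − 1 = 13.6%. The other fasted CV in that section, 198% for DIC, gives s = 1.262, SD = 0.258, about 29%; the protocol itself calls those fasted results lower than typical.
- *Full overlap:* participant effects cancel and s is the within-participant SD. AUC: 0.2041 × 0.34 = 0.0694, or 7.2%. Cmax: 0.2041 × 0.38 = 0.0776, or 8.1%.

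The count shown would be 12 + 12 = 24 from as few as 12 people.

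**6. The listing.** Protocol Tables 3 and 4 have 14 nominal times, so a person in both Parts under one ID would have 28 rows under B. A sort order need not be unique, and the listing also carries actual times.

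**The case for a change.** The best case for a change starts from the SAP's role as the detailed methodology: a programmer should not have to go back to the protocol to learn which B records to use. SAP Tables 2 and 3 label the arms Sequence 1 and Sequence 2 in both Parts, so shared codes are conceivable. With shared codes and both Parts' data admitted, the extra records would no longer drop out: over between-participant log SDs of 0.30 to 0.92, the SE for log(D/B) would fall to between 0.120 and 0.137. A hypothetical 25% higher fasted exposure in Part 1 would then multiply the D/B ratio by 0.89 to 0.99. The two-coefficient contrast does not exclude this, since it proves a cut by treatment but not a cut by Part.

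The arithmetic is right, but it needs two departures at once: pooling across Parts, against protocol 9.3.3.2, and treating AB and BD as one sequence. Neither is what the plan says.

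The display point has more substance, because SAP section 6 does not say whether B is split. Still, protocol 9.3.1 asks for separate reporting of arms, and the arm tables in protocol 6.1 list Treatment B once under each Part. The same reading that settles the models therefore points to showing B by Part. Whether a returning participant keeps one ID is not settled: protocol 6.3 assigns numbers at screening, 8.1 screens for each Part, and 10.1.4 speaks of a single code per participant.

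**Conclusion.** The wording gap is real, but it is a gap in detail that analysts fill sensibly. The plan followed as written gives within-Part food-effect estimates with the precision stated in Table 9, and no planned ratio or interval is affected.

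The remaining uncertainty concerns presentation of the Treatment B row and curves. At worst a pooled row would hold 24 records and sit away from the Part-specific geometric mean by a chance SD of about 14% without overlap (29% at the atypical DIC value), or 7% to 8% with full overlap. These figures assume 12 people per Part, no true difference between Parts, and variability borrowed from other presentations or from the protocol's sample-size section. Even then the models would still yield their own Part-specific adjusted means for B, and the ratios would be unchanged. Naming the Part would be a harmless editorial courtesy, but the analysis does not depend on it.
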